3.7.2 Statistical hypothesis, model, and method of analysis

All secondary efficacy endpoint analyses will be analyzed using the EES.

- **Overall Response Rate at Day 14**

Overall response rate at Day 14 will be calculated based on the local investigators review of aGvHD assessment data. They will be summarized using descriptive statistics (N, %) with two-sided exact binomial 90% CIs [Clopper and Pearson 1934].

- **Best Overall Response (BOR)**

BOR up to and including Day 28 will be calculated based on the local investigators review of aGvHD assessment data. They will be summarized using descriptive statistics (N, %) with two-sided exact binomial 90% CIs [Clopper and Pearson 1934]. BOR up to cut-off date will also be analysed in the same way.

- **Duration of response (DOR)**

The estimated cumulative incidence rates and 95% confidence intervals at 1, 2, 6, 12, 18 and 24 months will be presented. The cumulative incidence curve will be plotted. DOR will be summarized for all patients in the EES with overall response of CR or PR at Day 28.

- **Overall survival (OS)**

The OS distribution will be estimated using the Kaplan-Meier method, and the Kaplan-Meier curves, medians, 1, 2, 6, 12, 18 and 24 month survival estimates and 95% confidence intervals [Brookmeyer and Crowley 1982] will be presented.

- **Event Free Survival (EFS)**

The EFS distribution will be estimated using the Kaplan-Meier method, and the Kaplan-Meier curves, medians, 1, 2, 6, 12, 18 and 24 month survival estimates and 95% confidence intervals [Brookmeyer and Crowley 1982] will be presented.

- **Failure Free Survival (FFS)**

Cumulative incidence curve for FFS as well as estimates at 1, 2, 6, 12, 18 and 24 months with 95% confidence intervals will be presented, accounting for onset of chronic GvHD as the competing risk.

In addition, the cumulative incidence of each of the three components considering the other two components as a competing risks will be estimated. Onset of chronic GvHD is considered as a competing risk for all three types of failure.

- **Non-relapse mortality (NRM)**

The cumulative incidence curve for NRM as well as estimates at 1, 2, 6, 12, 18 and 24 months with 95% confidence intervals will be presented.

- **Incidence of Malignancy Relapse/Progression (MR)**

The cumulative incidence curve for MR and estimates at 1, 2, 6, 12, 18 and 24 months with 95% confidence intervals will be presented for patients with underlying hematologic malignant disease, accounting for NRM as the competing risk.

- **Cumulative steroid dosing until Day 56**

Overall and weekly cumulative steroid dose for each patient up to Day 56 or discontinuation of study treatment will be tabulated. In addition, the relative dose intensity (RDI), by week, will be calculated relative to the starting dose of corticosteroids and categorized as (1) complete reduction where patients are tapered off corticosteroids by D56, (2) $\leq 50\%$ RDI and (3) $> 50\%$ RDI. The proportion of patients in each category and corresponding 95% confidence intervals will be presented.

- **Incidence of cGvHD**

The cumulative incidence of cGvHD and estimates at 1, 2, 6, 12, 18 and 24 months with 95% confidence intervals will be presented, accounting for deaths without prior onset of cGvHD and hematologic disease relapse/progression as the competing risks. The cumulative incidence curve will be plotted.

- **Graft failure**

Summary statistics of graft failure assessment will be presented over time and at any timepoint by dose level and for all patients. In case of very few patients with graft failure (e.g. less than 5 patients), descriptions using only listings will be provided instead.

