7. Phase II To measure the activity of ruxolitinib in patients with aGvHD or SR-aGvHD assessed by Overall Response Rate (ORR) at Day 28.	8. Overall response rate (ORR) at Day 28, defined as the proportion of patients demonstrating a complete response (CR) or partial response (PR) without requirement for additional systemic therapies for an earlier progression, mixed response or non-response. Scoring of response will be relative to the organ stage at the start of the study treatment.
Secondary objective(s)	Endpoint(s) for secondary objective(s)
9. Key Secondary To assess the rate of durable ORR at Day 56	10. Proportion of all patients who achieve a CR or PR at Day 28 and maintain a CR or PR at Day 56
11. To estimate ORR at Day 14	12. Proportion of patients who achieved OR (CR+PR) at Day 14
13. To assess pharmacokinetic/pharmacodynamic relationships	14. PK parameters (such as AUC, Cmax, Ctrough) versus safety, efficacy, and PD biomarkers, as appropriate
15. To assess Duration of response	16. Duration of response (DOR) is assessed for responders only and is defined as the time from first response until aGvHD progression or the date of additional systemic therapies for aGvHD. Onset of chronic GvHD, or death without prior observation of aGvHD progression are considered as competing risks
17. To assess the cumulative steroid dose until Day 56	18. Weekly cumulative steroid dose for each patient up to Day 56

Objective(s)	Endpoint(s)
19. To evaluate the safety and tolerability of ruxolitinib	20. Safety and tolerability including myelosuppression, infections, and bleeding will be assessed by monitoring the frequency, duration and severity of Adverse Events including occurrence of any second primary malignancies, infections, by performing physical exams, and evaluating changes in vital signs from baseline, routine serum chemistry, hematology results and coagulation profile
21. To assess Overall Survival (OS)	22. Overall survival, defined as the time from the start of treatment to the date of death due to any cause
23. To assess Event-Free Survival (EFS)	24. Event-free survival, defined as the time from start of treatment to the date of hematologic disease relapse/progression, graft failure, or death due to any cause
25. To assess Failure-Free Survival (FFS)	26. Failure-free survival, defined as the time from the start of treatment to date of hematologic disease relapse/progression, non-relapse mortality, or addition of new systemic aGvHD treatment

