6.1.5 Treatment duration

The planned duration of aGvHD treatment is 24 weeks (approximately 6 months).

The Treatment Period for each patient will begin on Study Day 1 and continue until the end of Week 24, unless treatment change for any reason including treatment failure, e.g. aGvHD progression, mixed response, or no response, or aGvHD flare failure as defined in [Section 8.4.1.2](#), intolerable toxicity, death, or withdrawal from the study for other reasons occurs.

During the Treatment period, and beyond Day 28, patient's treatment will be managed according to their response as follows:

For patients with response at Day 28 (see [Table 8-3](#)):

- Patients responding to ruxolitinib will continue ruxolitinib until Day 56. These patients may be tapered off ruxolitinib as needed, starting no earlier than Day 56. The dose tapering strategy should be based on evaluation of the condition of the subject, current dosing regimen and the clinical judgment of the Investigator. (see [Section 6.1.5.1](#).)
- If a taper of ruxolitinib is considered appropriate, the taper should be completed no later than Week 24 unless prolonged tapering is indicated due to an aGvHD flare or other safety concern (see [Section 6.1.5.1](#)).

For patients with a lack of response at Day 28 (see [Table 8-3](#)):

- Patients must discontinue study treatment and be treated per Investigator's judgement. These patients will then enter the long-term follow-up period.

Patients responding to treatment will be tapered off immunosuppression (corticosteroids and CNI) as described in [Section 6.1.5.1](#).

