In addition, the proportion of patients who had hematologic malignancy relapse/progression and its 95% confidence interval will be presented for patients with underlying hematologic malignant disease.

- Best Overall Response (BOR)

Best overall response rate, is defined as the proportion of patients with complete response (CR) or partial response (PR) at any time point (up to and including Day 28 and before the start of additional systemic therapy for aGvHD).

- Cumulative steroid dosing until Day 56

Overall and weekly cumulative steroid dose for each patient up to Day 56 will be tabulated.

- Incidence of cGvHD

cGvHD is defined as the diagnosis of any cGvHD including mild, moderate, severe. Incidence of cGvHD is the time from the start of treatment to onset of cGvHD. Cumulative incidence of cGvHD will be estimated, accounting for deaths without prior onset of cGvHD and hematologic disease relapse/progression as the competing risks. If a patient is not known to have event or competing risks, then the incidence of cGvHD will be censored at the latest date the patient was known to be alive (on or before the cut-off date).

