3.1.1 General definitions

Investigational drug and study treatment

Investigational drug/study treatment, will refer to the ruxolitinib in this single arm study.

Date of first administration of study treatment

The date of first administration of study treatment is derived as the first date when a nonzero dose of study treatment was administered as per the DAR eCRF. The date of first administration of study treatment will also be referred as *start of investigational drug*.

Date of last administration of study treatment

The date of last administration of study treatment is defined as the last date when a nonzero dose of study treatment was administered as per DAR eCRF. The date of last administration of study treatment will also be referred as *end of investigational drug*.

Study day

The study day, describes the day of the event or assessment date, relative to the reference start date.

The study day is defined as:

- The date of the event (visit date, onset date of an event, assessment date etc.) – reference start date + 1 if event is on or after the reference start date;
- The date of the event (visit date, onset date of an event, assessment date etc.) – reference start date if event precedes the reference start date.

The reference start date for all assessments (e.g. safety, efficacy, PK, [REDACTED], etc.) is the start of study treatment.

The study day will be displayed in the data listings. If an event starts before the reference start date, the study day displayed on the listing will be negative.

Time unit

A year length is defined as 365.25 days. A month length is 30.4375 days (365.25/12). If duration is reported in months, duration in days will be divided by 30.4375. If duration is reported in years, duration in days will be divided by 365.25.

Baseline

For safety and efficacy evaluations, the last available assessment on or before the date of start of study treatment is defined as “baseline” assessment.

If patients have no value as defined above, the baseline result will be missing.

On-treatment assessment/event and observation periods

The overall observation period will be divided into three mutually exclusive segments:

1. ***pre-treatment period***: from day of patient’s informed consent to the day before first administration of ruxolitinib
2. ***on-treatment period***: from date of first administration of study treatment to 30 days after date of last actual administration of ruxolitinib (including start and stop date)

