Event-free survival is defined as the time from the study treatment start date to the date of hematologic disease relapse/progression, graft failure or death due to any cause. If a patient is not known to have any event, then EFS will be censored at the latest date the patient was known to be alive (last contact date on or before the cut-off date).

- **Failure Free Survival (FFS)**

Failure-free survival is defined as the time from the study treatment start date to date of hematologic disease relapse/progression, non-relapse mortality (NRM) or addition of new systemic aGvHD treatment. Each type of failure as a competing risk for the other two, and onset of chronic GvHD is considered as a competing risk for all three types of failure. If a patient is not known to have any event or competing risk, then FFS will be censored at the latest date the patient was known to be alive (last contact date on or before the cut-off date).

- **Non-relapse mortality (NRM)**

Non-relapse mortality is defined as the time from the study treatment start date to date of death not preceded by hematologic disease relapse/progression. Hematologic disease relapse/progression is considered a competing risk for NRM with the date of hematologic disease relapse/progression being the earlier of documented hematologic disease relapse/progression or institution of therapy to treat potential hematologic disease relapse/progression. If a patient is not known to have died or to have relapsed/progressed, then NRM will be censored at the latest date the patient was known to be alive (last contact date on or before the cut-off date).

- **Incidence of Malignancy Relapse/Progression (MR)**

Malignancy relapse/progression is defined as the time from the study treatment start date to date of hematologic malignancy relapse/progression. Deaths not preceded by hematologic

malignancy relapse/progression are competing risks. If a patient is not known to have event or competing risks, then MR will be censored at the latest date the patient was known to be alive (last contact date on or before the cut-off date).

- **Cumulative steroid dosing until Day 56**

The weekly cumulative steroid dose will be calculated for each patient up to Day 56 and the overall cumulative steroid dose will be calculated for each patient at Day 56. In addition, the proportion of patients with any dose reduction and any dose reduction of at least 50% in corticosteroids from baseline until EOT will be provided.

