Sample size	Minimum No. of responders	Response Rate	Probability to have a 90% CI with lower limit $\geq 60\%$	90% CI	
37	28	0.76	0.809	0.614	0.867
38	29	0.76	0.784	0.623	0.871
39	29	0.74	0.859	0.604	0.854
40	30	0.75	0.839	0.613	0.858
41	31	0.76	0.818	0.621	0.861
42	31	0.74	0.882	0.604	0.846
43	32	0.74	0.864	0.612	0.849
44	33	0.75	0.846	0.620	0.853
45	33	0.73	0.901	0.604	0.838
46	34	0.74	0.886	0.612	0.842
47	35	0.74	0.869	0.619	0.846
48	35	0.73	0.916	0.604	0.832
49	36	0.73	0.903	0.612	0.835
50	37	0.74	0.889	0.619	0.838

5 Change to protocol specified analyses

No change from protocol

6 Appendix

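### SAP 3.7.2 stops counting steroid dose when ruxolitinib stops, although the protocol and SAP 3.7.1 count it to Day 56

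*SAP*

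**What the plan says.** Protocol Table 2-1 defines the endpoint as "Weekly cumulative steroid dose for each patient up to Day 56". Protocol 12.5.1 plans the table in the same terms: "Overall and weekly cumulative steroid dose for each patient up to Day 56 will be tabulated". SAP Table 2-3 repeats the protocol's endpoint, and SAP 3.7.1 states that "the overall cumulative steroid dose will be calculated for each patient at Day 56". None of these four places ends the count earlier.

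SAP 3.7.2, the analysis paragraph for the same endpoint, does: "Overall and weekly cumulative steroid dose for each patient up to Day 56 or discontinuation of study treatment will be tabulated". SAP 3.1.1 fixes the meaning of study treatment: "Investigational drug/study treatment, will refer to the ruxolitinib in this single arm study". SAP section 5, which should list departures from the protocol, reads "No change from protocol".

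The stopping rules are in protocol 6.1.5. "Patients responding to ruxolitinib will continue ruxolitinib until Day 56". For patients with lack of response at Day 28, "Patients must discontinue study treatment and be treated per" the investigator's judgement. Protocol 6.1.5.1.1 and 9.1.1 also require a stop when new systemic aGvHD therapy is needed.

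SAP 3.4.2.4 separately plans a Safety Set summary of cumulative steroid dose to Day 28, Day 56 and the end of the on-treatment period. It takes doses after the end of treatment from the Prior and Concomitant Medications eCRF.

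**The concern.** SAP 3.7.1 and 3.7.2 define the same total differently, and nothing says which governs. Two programmers could each follow the SAP and produce different tables.

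The difference is not neutral. A patient who fails at Day 28 must leave ruxolitinib, and that is when SAP 3.7.2 stops counting that patient's steroid. A responder is counted for the full 56 days. Protocol 1.2 names steroid sparing as an expected benefit, so a total that omits steroid given after failure makes the result look better.

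SAP 3.7.2 also leaves two things open. It does not say whether weeks after a stop are missing or zero. It also does not say how a patient cut at Day 28 is placed in the three relative-dose-intensity categories (off steroids by Day 56, at most 50%, above 50%), which are reported as proportions with 95% confidence intervals.

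**Working it through.** The documents give no figure for this endpoint, so there is none to reproduce. The direction follows from the definition; the size can only be illustrated.

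**Direction.** Let d(t) ≥ 0 be the daily dose and T the day ruxolitinib stops. If T < 56, the sum of d(t) to T cannot exceed the sum to Day 56. The two are equal only if no steroid is given between T and Day 56. SAP 3.7.2 does not say whichever comes first; its heading, which ends the count at Day 56, makes that the natural reading, and I rely on it.

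**Inputs for the illustration**, in multiples of the starting daily dose D:

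- Responder: the example taper in protocol 6.1.5.1, a 10% reduction every 5 days from Day 7. Sum to Day 56 = 6 + 5 × (0.9 + 0.8 + … + 0.1) = 28.5.
- Non-responder (assumed): full dose to Day 28, then ruxolitinib stops. Counted under SAP 3.7.2: 28.0.
- Non-responder's dose on Days 29–56 (assumed): none, 0; 20% of D, 5.6; 50% of D, 14.0; the same taper started on Day 29, 5 × (0.9 + 0.8 + 0.7 + 0.6 + 0.5) + 3 × 0.4 = 18.7; full dose, 28.0.
- Response rate p: 80% (the planning assumption in protocol 12.8.1); 62% (the ruxolitinib arm of the phase III trial in protocol 1.1.2.1.2); 55% (the review cited in protocol 12.8.1).

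**Formulas.** Mean with the cut = 28.5p + 28.0(1 − p). Mean to Day 56 = that value + (1 − p) × the dose on Days 29–56. Understatement = 1 − (mean with the cut ÷ mean to Day 56).

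| p | Mean with cut | Mean to Day 56: none / 20% / 50% / taper / full | Understatement |
|---|---|---|---|
| 80% | 28.40 | 28.40 / 29.52 / 31.20 / 32.14 / 34.00 | 0 / 3.8 / 9.0 / 11.6 / 16.5% |
| 62% | 28.31 | 28.31 / 30.44 / 33.63 / 35.42 / 38.95 | 0 / 7.0 / 15.8 / 20.1 / 27.3% |
| 55% | 28.28 | 28.28 / 30.80 / 34.58 / 36.69 / 40.88 | 0 / 8.2 / 18.2 / 22.9 / 30.8% |

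For one non-responder kept on full dose, the cut lowers the total from 56D to 28D, about the same as a tapering responder's 28.5D.

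**Sensitivity.** If non-responders had first responded and tapered, they reach 6 + 5 × (0.9 + 0.8 + 0.7 + 0.6) + 2 × 0.5 = 22.0 by Day 28. At 80% the mean with the cut is 27.2, against 28.32, 30.0 and 32.8 for later dosing at 20%, 50% and full dose. The understatement is 4.0, 9.3 and 17.1%.

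**Weekly values can move either way.** In Week 8 (Days 50–56) a responder takes 2 × 0.1 = 0.20D. If weeks after a stop are missing, the Week 8 mean is 0.20D. For all patients at 80% response it is 0.8 × 0.20 + 0.2 × (0 / 1.4 / 3.5 / 3.2 / 7.0) = 0.16 / 0.44 / 0.86 / 0.80 / 1.56D for none / 20% / 50% / taper / full.

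**Data reach.** Protocol Table 8-1 collects concomitant medication until safety follow-up, 30 days after the last dose (protocol 9.1.5). A last dose on Day 26 gives 26 + 30 = Day 56, so collection may end before Day 56 for earlier stops.

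**The case against.** The strongest reply is that this is one stray phrase against four consistent definitions, so probably a drafting slip, and that the uncut total is already planned in SAP 3.4.2.4. Enrolment closed at 45 patients, all in Groups 1–3, and at least 45 were to be treated at the RP2D. The Safety Set is therefore probably nearly the Efficacy Evaluable Set used for this endpoint. That softens the point but does not remove it. SAP 3.4.2.4 plans no weekly cumulative dose and leaves the endpoint table cut. The report could then show two Day 56 totals for almost the same patients with no stated reason for the gap.

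An on-treatment sum is also a legitimate quantity, since later steroid reflects next-line management. That is fair, but it is not the quantity the protocol defines, and the change is not declared.

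The illustration deserves caution. The 62% and 55% rates come from other populations. Every non-responder is assumed to stop on Day 28 and survive to Day 56, and deaths would shrink the gap. Adverse events, cGvHD and other reasons also stop ruxolitinib, so not every patient cut is a treatment failure.

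Finally, the follow-up path after an early stop is not fully settled. Protocol 6.1.5 sends Day 28 non-responders to long-term follow-up, whose visits start at Month 12. Table 8-1 footnote 3 keeps early stoppers on the visit schedule, and 8.4.1.2 continues weekly disease assessment to Day 56 off treatment. The latter two support collecting the data, but the sections should be reconciled.

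**Conclusion.** The concern holds. SAP 3.7.2 contradicts the protocol and SAP 3.7.1 on when counting ends, and SAP section 5 does not declare the change. That the overall sum is lower or unchanged is certain on the earlier-of-two-dates reading. That the cut falls more on treatment failures is an inference from the stopping rules; no document gives the mix of reasons for stopping. The true size is unknown and could be zero. At the planned 80% response rate, with full dose to Day 28, the illustration runs from 0 to 16.5%. No formal hypothesis test depends on this endpoint. It should be corrected before the tables are produced because steroid sparing is a claimed benefit.

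**What to change.** In SAP 3.7.2, delete the words that end the count at discontinuation. Then specify:

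- **Sum.** Systemic corticosteroids from Day 1 to Day 56, or to death or withdrawal of consent if earlier, for every patient in the Efficacy Evaluable Set. Use the study-treatment eCRF to the end of treatment and the Prior and Concomitant Medications eCRF afterwards, as in SAP 3.4.2.4. Reconcile this with protocol 6.7.1.2, which asks for all steroid dose changes during the study on the Dose Administration Record eCRF.
- **Collection that ends before Day 56** (last ruxolitinib dose before about Day 26). Sum to the last collected date, report how many patients this affects, and show the mean with and without them. Report the number of deaths before Day 56 beside the table, because those totals are short as well.
- **Weekly table and categories.** State how weeks after a stop are shown. Place early stoppers in the relative-dose-intensity categories by their actual steroid dose to Day 56.
- **On-treatment version, if wanted.** Keep it as a labelled supportive table and declare it in SAP section 5.

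The cost is one deletion, one further data source that the SAP already names, and a short derivation rule. The reported steroid burden may be less favourable.

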3.7.3 Handling of missing values/censoring/discontinuations

Patients with missing assessments that prevent the evaluation of the ORR at Day 14 will be considered non-responders. This includes missing aGvHD assessments at baseline and/or Day 14. The time window for the Day 14 visit is defined in [Section 2.5.3](#).

3.8 Safety analyses

For all safety analyses, the safety set will be used. All listings and tables will be presented by group. If the Phase I starting dose is different to RP2D, the safety data will be listed and summarized by age group and dose level. For safety evaluations (except for AE), the last available assessment on or before the date of start of study treatment is taken as the “baseline” assessment.

Safety summaries (tables, figures) include only data from the on-treatment period with the exception of baseline data which will also be summarized where appropriate (e.g. change from baseline summaries). In addition, a separate summary for death including on treatment and post treatment deaths will be provided. In particular, summary tables for (AEs) will summarize only on-treatment events, with a start date during the on-treatment period (*treatment-emergent* AEs).

The on-treatment period lasts from the date of first administration of ruxolitinib to 30 days after the date of the last actual administration of ruxolitinib.

